11. ADVERSE EVENT REPORTING REQUIREMENTS

11.1 General

Adverse event collection and reporting is a routine part of every clinical trial. This study will use the descriptions and grading scales found in the CTEP Active Version of the NCI Common Terminology Criteria for Adverse Events (CTCAE) that is available at <http://ctep.cancer.gov/reporting/ctc.html> and the IWCLL criteria for hematologic malignancies as outlined in Section 6.3.1.

Information on all adverse events, whether reported by the participant, directly observed, or detected by physical examination, laboratory test or other means, will be collected, recorded, followed and reported as described in the following sections.

Adverse events experienced by participants will be collected and reported from initiation of study medication, throughout the study, and within 30 days of the last dose of study medication. Participants who experience an ongoing adverse event related to a study procedure and/or study medication beyond 30 days will continue to be contacted by a member of the study team until the event is resolved, stabilized, or determined to be irreversible by the participating investigator.

Participants should be instructed to report any serious post-study event(s) that might reasonably be related to participation in this study. The investigator should notify the IRB and any other applicable regulatory agency of any unanticipated death or adverse event occurring after a participant has discontinued or terminated study participation that may reasonably be related to the study.

11.2 Definitions

11.2.1 Adverse Event (AE)

An adverse event is any undesirable sign, symptom or medical condition or experience that develops or worsens in severity after starting the first dose of study treatment or any procedure specified in the protocol, even if the event is not considered to be related to the study.

11.2.2 Serious Adverse Event (SAE)

A serious adverse event is an undesirable sign, symptom, or medical condition which:

- is fatal or life-threatening;
- requires or prolongs inpatient hospitalization;
- results in persistent or significant disability/incapacity;
- constitutes a congenital anomaly or birth defect; or
- jeopardizes the participant and requires medical or surgical intervention to prevent one of the outcomes listed above.

Events **not** considered to be serious adverse events are hospitalizations for:

- routine treatment or monitoring of the studied indication, not associated with any deterioration in condition, or for elective procedures
- elective or pre-planned treatment for a pre-existing condition that did not worsen
- emergency outpatient treatment for an event not fulfilling the serious criteria outlined above and not resulting in inpatient admission
- respite care

11.2.3 Expectedness

Adverse events can be 'Expected' or 'Unexpected.'

11.2.3.1 Expected adverse event

Expected adverse events are those that have been previously identified as resulting from administration of the agent. For the purposes of this study, an adverse event is considered expected when it appears in the current adverse event list, the Investigator's Brochure, the package insert or is included in the informed consent document as a potential risk.

Refer to Section 6.1 for a listing of common expected adverse events associated with the study agent(s).

11.2.3.2. Unexpected adverse event

For the purposes of this study, an adverse event is considered unexpected when it varies in nature, intensity or frequency from information provided in the current adverse event list, the Investigator's Brochure, the package insert or when it is not included in the informed consent document as a potential risk.

11.2.4 Attribution

Attribution is the relationship between an adverse event or serious adverse event and the study treatment. Attribution will be assigned as follows:

- Definite – The AE is clearly related to the study treatment.
- Probable – The AE is likely related to the study treatment.
- Possible – The AE may be related to the study treatment.
- Unlikely - The AE is doubtfully related to the study treatment.
- Unrelated - The AE is clearly NOT related to the study treatment.

11.3 Recording Adverse Events

Adverse event information will be obtained at each contact with the participant. All adverse events will be recorded on the appropriate study-specific case report forms (CRFs).

11.4 Reporting Adverse Events

Each adverse event will be assessed to determine if it meets the criteria for serious adverse event. If a serious adverse event occurs, expedited reporting will follow local policies, and federal guidelines and regulations as appropriate.

It is the responsibility of the participating investigator to notify the Principal Investigator (or Protocol Chair), IRB, and others of all serious adverse events as required in the protocol.

The Principal Investigator (or Protocol Chair) will provide information with respect to adverse events and safe use of the study treatment (e.g., safety reports, Action Letters) to all participating investigators as soon as the information becomes available.

11.5 Sponsor Notification by Investigator

11.5.1 Serious Adverse Event Reporting Requirements

All events meeting the criteria for Serious Adverse Event (see Section 11.2.2) that occur after the initial dose of study treatment, during treatment, or within 30 days of the last dose of treatment must be reported as serious adverse events. Grade 4 hematologic toxicities are excluded from SAE reporting after the first cycle. Grade 4 ALC reporting is excluded from SAE reporting during all cycles.

The participating investigator must report each serious adverse event, regardless of attribution, to the Principal Investigator (or Protocol Chair) within 24 hours of learning of the occurrence. In the event that the participating investigator does not become aware of the serious adverse event immediately (e.g., participant sought treatment elsewhere), the participating investigator is to report the event within 24 hours after learning of it and document the time of his or her first awareness of the adverse event. Report serious adverse events by telephone and facsimile to:

[name] [contact] [contact]

Within the following 24-48 hours, the participating investigator must provide follow-up information on the serious adverse event. Follow-up information should describe whether the event has resolved or continues, if and how the event was treated, and whether the participant will continue or discontinue study participation.

11.5.2 Non-Serious Adverse Event Reporting Requirements

Non-serious adverse events will be reported to the Principal Investigator (or Protocol Chair) on the toxicity Case Report Forms.

11.6 Institutional Review Board (IRB) Notification by Investigator

The participating investigator will report all adverse events and serious adverse events to the Principal Investigator (or Protocol Chair) and to the IRB according to the local IRB's policies and procedures in reporting adverse events.

In the event of a multi-center study, the Principal Investigator (or Protocol Chair) will report adverse events and serious adverse events from all participating sites to the DFCI IRB according to the IRB's policies and procedures in reporting adverse events.

11.7 Food and Drug Administration (FDA) Notification by Sponsor-Investigator

The Sponsor-Investigator will report to the FDA any adverse event that is serious, unexpected and reasonably related (i.e., possible, probable, definite) to the study treatment.

Unexpected fatal or life-threatening experiences associated with the use of the study treatment will be reported to FDA as soon as possible but in no event later than 7 calendar days after initial receipt of the information.

All other serious unexpected experiences associated with the use of the study treatment will be reported to FDA as soon as possible but in no event later than 15 calendar days after initial receipt of the information.

Events will be reported to the FDA by telephone ([name]) or by fax ([name]) using Form FDA 3500A (Mandatory Reporting Form for investigational agents) or FDA Form 3500 (Voluntary Reporting Form for commercial agents). Forms are available at <http://www.fda.gov/medwatch/getforms.htm>.

11.8 Hospital Risk Management Notification by Investigator

The participating investigator will report to the Principal Investigator (or Protocol Chair) and to local Risk Management any subject safety reports or sentinel events that require reporting according to institutional policy.

12. DATA AND SAFETY MONITORING

12.1 Data Reporting

12.1.1 Method

The QACT will collect, manage, and monitor data for this study.

12.1.2 Data Submission

The schedule for completion and submission of case report forms (paper or electronic) to the QACT is as follows:

Form	Submission Timeline
Eligibility Checklist	Complete prior to registration with QACT

On Study Form	Within 14 days of registration
Baseline Assessment Form	Within 14 days of registration
Treatment Form	Within 10 days of the last day of the cycle
Adverse Event Report Form	Within 10 days of the last day of the cycle
Response Assessment Form	Within 10 days of the completion of the cycle required for response evaluation
Off Treatment/Off Study Form	Within 14 days of completing treatment or being taken off study for any reason
Follow up/Survival Form	Within 14 days of the protocol defined follow up visit date or call

12.2 Safety Meetings

The DF/HCC Data and Safety Monitoring Committee (DSMC) will review and monitor toxicity and accrual data from this trial. The committee is composed of clinical specialists with experience in oncology and who have no direct relationship with the study. Information that raises any questions about participant safety will be addressed with the Principal Investigator and study team.

The DSMC will meet quarterly and/or more often if required to review toxicity and accrual data. Information to be provided to the committee may include: up-to-date participant accrual; current dose level information; DLT information; all grade 2 or higher unexpected adverse events that have been reported; summary of all deaths occurring within 30 days for Phase I or II protocols; for gene transfer protocols, summary of all deaths while being treated and during active follow-up; any response information; audit results, and a summary provided by the study team. Other information (e.g. scans, laboratory values) will be provided upon request.

12.3 Monitoring

Involvement in this study as a participating investigator implies acceptance of potential audits or inspections, including source data verification, by representatives designated by the Principal Investigator (or Protocol Chair) or DF/HCC. The purpose of these audits or inspections is to examine study-related activities and documents to determine whether these activities were conducted and data were recorded, analyzed, and accurately reported in accordance with the protocol, institutional policy, Good Clinical Practice (GCP), and any applicable regulatory requirements.

All data will be monitored for timeliness of submission, completeness, and adherence to protocol requirements. Monitoring will begin at the time of participant registration and will continue during protocol performance and completion.

13. REGULATORY CONSIDERATIONS

13.1 Protocol Review and Amendments

This protocol, the proposed informed consent and all forms of participant information related to the study (e.g., advertisements used to recruit participants) and any other necessary documents must be submitted, reviewed and approved by a properly constituted IRB governing each study location.

Any changes made to the protocol must be submitted as amendments and must be approved by the IRB prior to implementation. Any changes in study conduct must be reported to the IRB. The Principal Investigator (or Protocol Chair) will disseminate protocol amendment information to all participating investigators.

All decisions of the IRB concerning the conduct of the study must be made in writing.

13.2 Informed Consent

All participants must be provided a consent form describing this study and providing sufficient information for participants to make an informed decision about their participation in this study. The formal consent of a participant, using the IRB approved consent form, must be obtained before the participant is involved in any study-related procedure. The consent form must be signed and dated by the participant or the participant's legally authorized representative, and by the person obtaining the consent. The participant must be given a copy of the signed and dated consent document. The original signed copy of the consent document must be retained in the medical record or research file.

13.3 Ethics and Good Clinical Practice (GCP)

This study is to be conducted according to the following considerations, which represent good and sound research practice:

- ICH Consolidated Good Clinical Practice: Guidelines (E6)
www.fda.gov/cder/guidance/iche6.htm
- US Code of Federal Regulations (CFR) governing clinical study conduct and ethical principles that have their origin in the Declaration of Helsinki

- Title 21 Part 11 – Electronic Records; Electronic Signatures
www.access.gpo.gov/nara/cfr/waisidx_02/21cfr11_02.html
 - Title 21 Part 50 – Protection of Human Subjects
www.access.gpo.gov/nara/cfr/waisidx_02/21cfr50_02.html
 - Title 21 Part 54 – Financial Disclosure by Clinical Investigators
www.access.gpo.gov/nara/cfr/waisidx_02/21cfr54_02.html
 - Title 21 Part 56 – Institutional Review Boards
www.access.gpo.gov/nara/cfr/waisidx_02/21cfr56_02.html
 - Title 21 Part 312 – Investigational New Drug Application
www.access.gpo.gov/nara/cfr/waisidx_02/21cfr312_02.html
- State laws
 - Institutional research policies and procedures
www.dfhcc.harvard.edu/clinical-research-support/clinical-research-operations-cro/policies-and-procedures

It is understood that deviations from the protocol should be avoided, except when necessary to eliminate an immediate hazard to a research participant. In such case, the deviation must be reported to the IRB according to the local reporting policy.

13.4 Study Documentation

The investigator must prepare and maintain adequate and accurate case histories designed to record all observations and other data pertinent to the study for each research participant. This information enables the study to be fully documented and the study data to be subsequently verified.

Original source documents supporting entries in the case report forms include but are not limited to hospital records, clinical charts, laboratory and pharmacy records, recorded data from automated instruments, microfiches, photographic negatives, microfilm or magnetic media, and/or x-rays.

13.5 Records Retention

All study-related documents must be retained for the maximum period required by applicable federal regulations and guidelines or institutional policies.

14. STATISTICAL CONSIDERATIONS

14.1 Primary Objectives

14.1.1 Primary Objectives for Phase I Trial

A standard 3+3 dose-escalation design is used in the Phase I portion for assessing the safety and determining the MTD and recommended dose for the Phase II portion of this study of pyrimethamine in relapsed CLL/SLL and T-LGL patients.

14.1.2 Primary Objectives for Phase II Trial

After MTD is established in Phase I, 20 additional patients will be enrolled in the Phase II study and treated with pyrimethamine at the MTD. The primary objective for this portion of the study is to determine the overall response rate of pyrimethamine in these patients, including both CLL/SLL and T-LGL.

14.2 Sample Size and Patient Accrual

14.2.1 Phase I

To assess the MTD of pyrimethamine, a standard 3+3 dose-escalation design is used, with 5 planned pyrimethamine dose levels (Section 5); the observation period is one cycle (28 days). 3 patients are enrolled in the study initially, if no DLT is observed in the first 3 patients at a given dose level of pyrimethamine, escalation will proceed. If 2 or 3 DLTs are observed in the first 3 patients, escalation stops. If 1 DLT is observed, an additional 3 patients will be enrolled at the same dose level. If no DLT is observed in the additional 3 patients, escalation proceeds. If any DLTs are observed among the 3 additional patients, escalation stops.

Based on this dose escalation scheme, the probability of escalating to the next dose level for various true underlying rates of DLT is given in Table 1.

Table 1 Probability of Escalation for Various True Underlying DLT Rates for Pyrimethamine

True DLT Rate	1.0%	10.0%	20.0%	30.0%	40.0%	50.0%
Probability of Escalation	0.99	0.91	0.71	0.49	0.31	0.17

If the true underlying proportion of DLT is 30% at the current dose during the treatment period, there is a 49% chance of escalating to the next dose. We anticipate that a minimum of 2 to a maximum of 12 additional patients will be enrolled in the Phase I portion of the study.

14.2.2 Phase II

The Phase II portion is a single arm study which consists of determining the overall response rate of pyrimethamine in relapsed CLL/SLL and T-LGL patients. The overall response rate is not expected to differ between these two diseases and therefore one overall response rate will be reported. A 35% overall response rate will be considered promising. The first response evaluation will be assessed after the first cycle of treatment then at the end of three cycles.

Six Phase I patients treated at the MTD of pyrimethamine will be enrolled in the Phase II part of the study. A Simon's two stage optimal design is used to compute the sample size. A total number of 26 patients is needed in order to detect a 35% response rate, assuming the ORR for the null hypothesis is 10%, with 90% power and 10% type I error. The study will stop early if only 1 or 0 responses out of the first 10 patients is observed, and the drug will not be declared promising if less than 5 responses are seen in the total 26 patients. The probability of stopping at the first stage if the true ORR is less than 35% is 0.736.

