3. PARTICIPANT SELECTION

3.1 Eligibility Criteria

Participants must meet the following criteria on screening examination to be eligible to participate in the study:

Subjects with CLL/SLL:

3.1.1 Subjects must be diagnosed with CLL / SLL (chronic lymphocytic leukemia / small lymphocytic lymphoma) based on the standard histologic and immunophenotypic criteria described in the WHO classification of lymphoid malignancies, including immunophenotypic confirmation that the tumor cells co-express B cell antigens CD19 / 20 and CD5. Mantle cell lymphoma should be excluded based on positive staining of the tumor cells for CD23, or the absence of staining of the tumor cells for cyclin D1 or the absence of t(11;14). This diagnosis should be confirmed at a Dana-Farber Harvard Cancer Center institution (DFCI, BWH, MGH, BIDMC) within approximately one month after the subject is registered. Any question on histology confirmation should be brought to the attention of the Principal Investigator.

3.1.2 Participants must have measurable disease, defined as lymphocytosis \geq 5,000 / ul, or at least one palpable or CT measurable lesion $>$ approximately 1.5 cm, or bone marrow involvement $>$ approximately 30%.

3.1.3 Subjects must have relapsed after at least one prior purine analogue-containing regimen (fludarabine, cladribine or pentostatin), OR at least two non-purine analogue containing regimens.

Subjects with T-LGL:

T-LGL judged by the investigator to require therapy based upon:

- 1) Severe neutropenia (absolute neutrophil count $<$ 500/microL)
- 2) Moderate neutropenia (absolute neutrophil count $<$ 1000/microL) with recurrent infections
- 3) Symptomatic or transfusion dependent anemia
- 4) Severe thrombocytopenia ($<$ 50,000/microL)
- 5) Hepatic infiltration resulting in abnormal liver function tests
- 6) Symptomatic splenomegaly

Patients with previously untreated or relapsed/refractory disease will be eligible

All Subjects:

3.1.4 Age \geq 18 years.

3.1.5 Life expectancy of greater than 3 months.

3.1.6 ECOG performance status \leq 2 (Karnofsky \geq 60%, see Appendix B).

3.1.7 Participants must have normal organ function as defined below:

- total bilirubin $\leq 1.5X$ institutional ULN unless due to indirect hyperbilirubinemia related to Gilbert's syndrome or hemolysis, or to disease infiltration
- AST (SGOT)/ALT (SGPT) $\leq 5 X$ institutional upper limit of normal
- creatinine $\leq 2X$ institutional ULN

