10. MEASUREMENT OF EFFECT

Responses will be formally assessed initially at the conclusion of the 1st 28 day cycle, then at the conclusion of three cycles (three months), and then every three months thereafter, until disease progression, start of another treatment, or death. Response will be assessed in two ways: (1) By NCI-WG 1996 criteria³ (as updated in the IWCLL 2008 criteria Section 10.2)¹⁹ without the use of CT scans. In this case lymph nodes will be assessed based on physical exam measurements; (2) With the incorporation of CT findings as suggested for clinical trials in IWCLL 2008. Thus CT scans will be performed on all patients at the end of the 1st month, 3rd month and 6th month, if still on study we will evaluate the impact of the CT scans (1) if used only to confirm CR; (2) if used to assess lymphadenopathy regardless of PE findings. After the 6 month evaluation, further CT scans will generally not be done, but may be done at the discretion of the treating physician.

Following the initial screening bone marrow biopsy, additional bone marrow biopsies will be performed only to confirm complete remission.

T-LGL Response Criteria²¹:

Response to treatment should be evaluated by history, physical examination, and complete blood count with differential:

- Complete response — A hematologic complete response is defined as the complete normalization of blood counts (ie, hemoglobin >12 g/dL; platelets >150,000/microL; absolute neutrophil count >1500/microL; absolute lymphocyte count <4000/microL) in the setting of a circulating LGL count of less than 500/microL.
- Partial response — A hematologic partial response is defined as an improvement in blood counts that does not meet criteria for complete remission (eg, an absolute neutrophil count >500/microL or decreasing transfusion requirements).
- Treatment failure — Treatment failure is defined as an inability to achieve an at least partial response after four months of therapy.
- Progressive disease — Progressive disease is defined as a worsening of cytopenias, hepatomegaly, or splenomegaly

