10.2 Antitumor Effect – Hematologic Tumors

Parameter	CR*	PR*	PD*
Group A			
Lymphadenopathy [^]	None > 1.5 cm	Decrease ≥50%	Increase ≥50%
Hepatomegaly	None	Decrease ≥50%	Increase ≥50%
Splenomegaly	None	Decrease ≥50%	Increase ≥50%
Blood lymphocytes	<4000/μL	Decrease ≥50% from baseline	Increase ≥50% over baseline
Marrow [#]	Normocellular, < 30% lymphocytes, no B-lymphoid nodules.	≥ 30% lymphocytes, or B-lymphoid nodules, or not done	Increase of lymphocytes to more than 30% from

			normal.
	Hypocellular marrow defines CRi		
Constitutional Symptoms@	None	Any	Any
Group B			
Platelet count	> 100 000/ μ L	> 100 000/ μ L or increase \geq 50% over baseline	Decrease of \geq 50% from baseline secondary to CLL
Hemoglobin	> 11.0 g/dL (untransfused and w/o erythropoietin)	> 11 g/dL or increase \geq 50% over baseline	Decrease of > 2 g/dL from baseline secondary to CLL
Neutrophils#	> 1500/ μ L	> 1500/ μ L or > 50% improvement over baseline	Any

* CR (complete remission): all of the criteria have to be met, and patients have to lack disease-related constitutional symptoms

* PR (partial remission): at least two of the criteria of group A plus one of the criteria of group B have to be met. PR to be held at least two months and confirmed by restaging.

* SD is absence of progressive disease (PD) and failure to achieve at least a PR; PD: at least one of the above criteria of group A or group B has to be met.

^Sum of the products of multiple lymph nodes (as evaluated by CT scans in clinical trials, or by physical examination in general practice).

#These parameters are irrelevant for some response categories.

@Constitutional symptoms: Unintentional weight loss \geq 10% within the previous 6 months, significant fatigue (ECOG PS 2 or worse, Fevers >100.5F or 38.0 C for 2 or more weeks without other evidence of infection, night sweats >1 month without evidence of infection

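### One pooled response rate is planned for CLL/SLL and T-LGL, so the report would not show whether a promising result came from only one disease

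*Combined protocol and SAP*

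**What the plan says.** Section 14.2.2 states: "The overall response rate is not expected to differ between these two diseases and therefore one overall response rate will be reported". Section 14.1.2 sets the Phase II objective for both diseases together, and Section 14.3 plans one ORR with one 90% interval by a two-stage method.

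Sections 1.3, 14.4 and 14.5 name no response rate by disease and no test of response by disease. The nearest item is the prognostic-factor analysis. It does not name disease type as a factor, and its objective covers CLL/SLL only in Section 14.4 (Section 1.3 adds T-LGL). Section 14.6.2 requires a response category for every participant.

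The two diseases are handled differently in two places:

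- **Prior treatment (Section 3.1).** CLL/SLL patients must have relapsed. For T-LGL: "Patients with previously untreated or relapsed/refractory disease will be eligible".
- **Partial response (PR).** For T-LGL, Section 10 says: "A hematologic partial response is defined as an improvement in blood counts that does not meet criteria for complete remission", with examples "an absolute neutrophil count >500/microL or decreasing transfusion requirements". No minimum change and no holding period is given. For CLL/SLL, Section 10.2 requires that "at least two of the criteria of group A plus one of the criteria of group B have to be met", and adds "PR to be held at least two months and confirmed by restaging".

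**The concern.** The plan reports a single rate because it expects the rates to be equal, but it cites no response data for that expectation. It gives a shared STAT3 rationale (Sections 2.2 and 2.3.1). The disease-specific cell data for pyrimethamine are in CLL (Section 2.3.3), and Section 2.2 itself says STAT3 mutations are not clearly known to predict response. A portion of text between Sections 2.3.4 and 2.4 was not available, so nothing is claimed about it.

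The plan also gives reasons why observed rates could differ whatever the biology: T-LGL patients may be untreated, and their PR is easier to reach. If T-LGL supplies most of the responders, a pooled success would read as support for the drug in both diseases, and the planned report would give no means of seeing otherwise.

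**Working it through.** **1. Reproduce the plan's own figures.** Section 14.2.2: null 10%, alternative 35%, stop at 0 or 1 responses in the first 10, promising at 5 or more of 26. With X1 ~ Bin(10, p) and X2 ~ Bin(16, p):

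- P(stop) = P(X1 ≤ 1). At 10% this is 0.9^10 + 10 × 0.1 × 0.9^9 = 0.3487 + 0.3874 = 0.736, the stated value.
- P(promising) = Σ over x = 2 to 10 of P(X1 = x) × P(X2 ≥ 5 − x). At 10% this is 0.079, within the 10% limit. At 35% it is 0.903, against the stated 90%.

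The pooled rule therefore performs as claimed when one rate applies to everyone.

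**2. Compare the PR definitions.** One T-LGL entry criterion is a neutrophil count below 500/microL, and a T-LGL PR example is a count above 500. A rise from 450 to 510 fits the example: (510 − 450)/450 = 13%. The CLL/SLL neutrophil line needs a count above 1500 or more than "50% improvement over baseline", which from 450 means above 1.5 × 450 = 675. Even that meets only the Group B part of a CLL/SLL PR.

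**3. What one pooled figure can hide.** At the minimum success, 5/26 = 19.2%. Exact (Clopper-Pearson) 90% intervals for one possible split:

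- T-LGL 3/5 = 60%: 18.9 to 92.4%
- CLL/SLL 2/21 = 9.5%: 1.7 to 27.1%

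**4. How often this matters.** The documents give neither the disease mix nor disease-specific rates for pyrimethamine, so these are assumed: 3, 5 or 8 T-LGL patients of 26; CLL/SLL truly at 10%; T-LGL at 20% or 38%. The 38% is the low end of the range Section 2.2 cites for other drugs. The pooled rule was enumerated exactly as the sum of two independent binomials per stage, with the T-LGL patients split at random over the stages (hypergeometric, 10 of 26 in stage 1). Fixed splits of 1+2, 2+3 and 3+5 change the probabilities in the table by at most about 0.01.

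A CLL/SLL 90% interval lies wholly below 35% for at most 3/23 (upper limit 30.4%), 3/21 (32.9%) or 2/18 (31.0%).

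| True rates (CLL/SLL, T-LGL) | P(promising), 3 / 5 / 8 T-LGL | CLL/SLL interval below 35%, given success |
|---|---|---|
| 10%, 20% | 0.11 / 0.14 / 0.18 | 15% / 35% / 29% |
| 10%, 38% | 0.18 / 0.27 / 0.43 | 32% / 58% / 53% |
| 10%, 10% | 0.079 in each | 5% / 16% / 10% |
| 35%, 35% | 0.903 in each | 0.3% / 1.2% / 1.0% |

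P(promising) shows how a mixed population moves the pooled verdict; a by-disease report does not change it. The last column shows how often such a report would reveal a low CLL/SLL rate behind a success.

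A cruder measure is at most 2 CLL/SLL responders, given success. With 3, 5 and 8 T-LGL patients this occurs in 1%, 9% and 29% (T-LGL at 20%) or 6%, 25% and 53% (T-LGL at 38%).

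**The case against.** The strongest reply is that nothing is wrong with the test. The plan makes a stated choice, gives a reason, and defines its objective over both diseases. Stating one rate does not forbid a descriptive split. Response is recorded per participant, and the CLL/SLL prognostic-factor and CT analyses would partly expose where responses came from. On this view only a minor descriptive line is missing.

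The size measure can also be attacked. An interval below 35% is not a protocol criterion, and a pooled 5/26 has an exact 90% interval of 7.9 to 36.3%, so a minimal success barely reaches 35% anyway. The measure is discrete and erratic: with only 2 T-LGL patients it flags 37% (T-LGL at 20%) or 53% (T-LGL at 38%) of successes, because 4/24 has an upper limit of 34.2% and is flagged while 4/23 at 35.5% is not. With every patient at 10% it still flags 5 to 22% of successes across 2 to 8 T-LGL patients.

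Much of this stands. The test is valid, the percentages should be read as rough, and the 3/5 against 2/21 split is an illustration. But a low CLL/SLL interval when CLL/SLL is truly at 10% is not a misleading signal, even if T-LGL is equally low. The main point also does not rest on this measure. The plan says one rate will be reported, and none of the other analyses commits the sponsor to an ORR by disease. A split chosen after the results are known carries less weight than one specified now.

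**Conclusion.** The concern holds. Followed as written, the plan gives a pooled primary result that cannot show whether a promising verdict came from one disease, although the diseases differ in entry rules and in how a PR is scored. This affects interpretation of the primary endpoint, not the validity or error rates of the decision rule, and it should be fixed.

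Its size depends on unknown disease-specific rates and on the T-LGL share. It is small if few T-LGL patients enrol and grows with their number and response rate. The absence of a planned ORR by disease and the unequal PR definitions depend on none of these assumptions.

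**What to change.** Keep the pooled decision rule, the pooled ORR and its two-stage interval.

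- In Section 14.2.2, replace the closing clause that commits to a single reported rate with: *and the decision rule is therefore applied to the pooled overall response rate.*
- In Section 14.3, add: *ORR (responders/patients) with an exact binomial 90% confidence interval will also be reported separately for CLL/SLL and for T-LGL, as a descriptive analysis.*

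The two-stage interval method stays for the pooled ORR only. The by-disease intervals ignore the early-stopping rule, because stage sizes by disease are not fixed, and should be labelled descriptive for that reason.

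The cost is one clause, one sentence and two summary lines, with no extra patients, no new data and no change to the rule. The drawback is imprecision in T-LGL: 3/7, for example, gives about 13 to 77%.
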